### 2.2 Purpose

This Statistical Analysis Plan (SAP) describes the planned analysis and reporting of BOSS-001 study, which is a randomized, double-blind, place-controlled study of Black Seed Oil in treating Covid-19 patient on an outpatient basis.

# BOSS-Covid-19 Study (BOSS-001)

Also, exploratory analyses not necessarily identified in this SAP and/or specified in the corresponding protocol may be performed, should the investigating team and/or EC deem it necessary. Any post-hoc, or unplanned analyses not identified in this SAP will be clearly identified in the respective Clinical Study Report (CSR).

The following documents were reviewed and used as guiding references in preparation of this SAP:

- Clinical Research Protocol: BOSS-001 Version 6.0 dated 17 May 2021
- ICH E9: Statistical Principles for Clinical Trials (September 1998)
- E9 Statistical Principles for Clinical Trials Guidance document by FDA

Although we have quoted the relevant sections of the protocol in this SAP for convenience, the reader of this SAP is encouraged to also read the entire clinical protocol for details on the intervention and conduct of this study, and the operational aspects of clinical assessments and their timings subjects in this study.

## 3 Study Design

### 3.1 Overview

This is a randomized (1:1), double-blind, placebo-controlled phase 2 study to assess safety and efficacy of Total 3 g daily dose of Black Seed Oil ('TQ Formula ' this point forward) capsules versus placebo in treating patients who have tested positive for novel Coronavirus 2019 (Covid-19) in the outpatient setting.

Patients will be treated at a dose of 500 mg, 3 capsules, two times a day for 14 days from date of randomization.

Quantitative viral load as measured by RT-PCR will be evaluated at baseline and on days 7 and 14.

Covid-19 symptoms will be measured throughout the study using Modified FLU-PRO Plus.

### 3.2 Sample size

The total sample for this study is a minimum of 52 and up to 60 patients equally split between the placebo arm and the treatment arm.

The sample size is driven by the primary objective to compare the median time to sustained clinical response between the two arms.

For statistical analysis purposes, sustained clinical response is defined as a reduction to a score of <= 2 on all symptom scores on the Modified FLU-PRO Plus questionnaire and remaining <= 2 for

# BOSS-Covid-19 Study (BOSS-001)

at least three days. Time to sustained clinical response will be calculated from the date of testing to the first day all symptoms are  $\leq 2$ .

Power calculation will be based only on the first primary objective of the trial. Based on the median time to sustained clinical response reported by CDC [122], the expected median time to response in the placebo arm will be approximately 16 days from the onset of symptoms in outpatients. With a sample size of 20 in each arm, a difference in median time to sustained clinical response of 10 days between the intervention arm and the placebo arm will be able to be detected with 81.5% statistical power with 5% Type-1 error rate. Median time to sustained clinical response will be estimated based on 21-day follow-up. With an attrition expectation of around 20%, the planned accrual is 26 patients in each arm and potentially up to 30 patients.

## 3.3 Inclusion/Exclusion Criteria

### 3.3.1 Inclusion Criteria

In order to be eligible to participate in this study, an individual must meet all of the following criteria:

1. Provision of signed and dated informed consent form
2. Stated willingness to comply with all study procedures and availability for the duration of the study
3. Male or female, aged 18 and over, presenting with recent mild to moderate clinical symptoms of Covid-19 infection (per FDA guidance – see appendix 3)
4. Positive COVID-19 infection confirmed with a rapid antigen test at screening (or RT-PCR within the last 3 days) and confirmed with a RT-PCR test at baseline
5. A score of  $\geq 3$  on a minimum of 2 symptoms on the Modified FLU-PRO Plus
6. Ability to take oral medication and be willing to adhere to the dosing regimen (Twice a day – BID for 14 days)
7. For females of reproductive potential: negative pregnancy test at screening and use of highly effective contraception method during study participation and for an additional 4 weeks after the end of study drug administration
8. For males of reproductive potential: use of condoms or other methods to ensure effective contraception with partner during study participation
9. Agreement to adhere to Lifestyle Considerations (see section 5.3) throughout study duration

# BOSS-Covid-19 Study (BOSS-001)

## 3.3.2 Exclusion Criteria

An individual who meets any of the following criteria will be excluded from participation in this study:

- Current or recent (within 4 weeks) treatment with any corticosteroids; however, high-dose inhaled steroids, which are used to treat acute or chronic bronchial inflammation, will be permitted
- Current or recent (within 4 weeks) treatment with any antivirals
- Room air oxygen saturation (SaO2) < 94% at screen
- Walking oximetry < 90% or participant unable to complete 6-minute walking oximetry test at screen
- Severe Covid-19 symptoms (severe per FDA classification – see appendix 3)
- Requires immediate admission to hospital for any reason
- Pregnancy or lactation
- Known allergic reactions to components of black seed oil, or thymoquinone
- Treatment with another investigational drug or other investigational intervention within 2 weeks of study start and throughout study duration.
- Significant hepatic disease (ALT/AST > 4 times the ULN); any laboratory parameter >/= 4 times the ULN
- History of moderate to severe CKD, (i.e. an estimated glomerular filtration rate less than 45 mL/min) at the time of enrollment or history of liver disease
- Patients with inflammatory bowel disease (such as Crohn's) that could affect the intestinal absorption of TQ Formula enteric coated capsules.
- Known HIV or Hepatitis C infection
- Influenza diagnosis (confirmed by testing) during screening or within prior 14 days
- Any uncontrolled condition(s) or diagnosis, both physical or psychological, or physical exam finding that precludes participation, as per investigator
- Current treatment with CYP2C9 substrates

## 3.4 Randomization, Blinding, and Patient Selection

Study participants will be randomized in a one to one fashion (1:1) using a block randomization with a block size of 4 independently within each center to receive either 3 g/day of TQ Formula (500 mg capsules x 3, BID) or placebo capsules (identical in appearance to active product) for 14

# BOSS-Covid-19 Study (BOSS-001)

days. Participants will receive the full study supply (14-day medication) at randomization. Study capsules should be stored at ambient temperature (15°C to 25°C), away from direct sunlight. The study is double blinded; all subjects, investigators, and study personnel involved in the conduct of the study, including data management and primary biostatistician, will be blinded to treatment assignment. There will be an independent unblinded statistician. The unblinded study statistician will not otherwise participate in study procedures or data analysis.

A randomization list will be prepared by the unblinded statistician and provided to the investigational product (IP) depot for labelling. Sponsor and CRO study staff will remain blinded to study treatment. Randomization numbers will be assigned through the Electronic Data Capture (EDC) system.

Participants will complete a daily questionnaire on Covid-19 symptoms, which will be used to determine the primary endpoint for the study. For this reason, it is important that participants remain blinded to treatment allocation.

## Unblinding

In the unlikely event that unblinding is required, the principal investigator can contact the unblinded statistician to unblind treatment. Treatment unblinding is discouraged if knowledge of the treatment assignment will not materially change the planned management of a medical emergency. Unblinding should be discussed in advance with the medical monitor if possible. If the investigator is not able to discuss treatment unblinding in advance, then he/she must notify the medical monitor as soon as possible about the unblinding incident without revealing the participant's treatment assignment.

Final unblinding for the data analysis will not take place until and unless all data queries from data quality assessments are adequately addressed by each participating site.

## 3.5 Study Calendar and Data Collection

The schedule of the study visits and data to be collected are shown below.

**Table 1.** Schedule of events

Procedures	Day -3 to -1	Visit 1, Day 1	Day 4 +/- 1 day	Day 7 +/- 1 day	Day 10 +/- 1 day	Day 14 +/- 1 day	Day 21 +/- 1 day	Day 45 +/- 1 day
Informed consent	X							
Demographics	X							
Medical history	X							

# BOSS-Covid-19 Study (BOSS-001)

Inclusion/Exclusion Criteria Evaluation	X	X						
Rapid Antigen Test for Covid-19	X c							
RT-PCR sample for quantitative viral load analysis		X c		X		X		
Serum Collection (Blood sample for immune monitoring)		X		X		X		
Physical exam	X			X		X		
Vital signs	X	X		X		X		
Pulse Oximetry	X							
Walking Oximetry	X							

# BOSS-Covid-19 Study (BOSS-001)

Procedures	Day -3 to -1	Visit 1, Day 1	Day 4 +/- 1 day	Day 7 +/- 1 day	Day 10 +/- 1 day	Day 14 +/- 1 day	Day 21 +/- 1 day	Day 45 +/- 1 day
Height	X							
Weight	X							
Hematology	X		X e	X	X e	X		
Serum chemistry a	X		X e	X	X e	X		
Pregnancy test b	X							
Randomization		X						
Administer study intervention		X.....X						
Concomitant medication review	X	X	X	X	X	X	X	
Adverse event review/evaluation	X	X	X	X	X	X	X	X
Patient Reported Outcomes (Modified FLU-PRO Plus)*	X +	X.....X						
Complete Case Report Forms (CRFs)	X	X	X	X	X	X	X	

a: Albumin, alkaline phosphatase, total bilirubin, direct bilirubin, bicarbonate, BUN, calcium,

chloride, creatinine, glucose, LDH, phosphorus, potassium, total protein, AST, ALT, sodium,

CBC/diff, LDH, , CRP, prothrombin time, activated partial prothrombin time, , D-dimer b:

Serum pregnancy test (women of childbearing potential).

c: Covid-19 Confirmatory test in addition to quantitative viral load d:

Screening and Baseline can be combined

e: If clinically indicated at the discretion of the investigator

f: Visits at Day 4 (visit 2), Day 10 (visit 4), and Day 21 (final visit) will be telehealth and can be changed to in-person at the discretion of the investigator

g: In the event of a complete lockdown due to Covid, visits at Day 7(Visit 3) and Day 14 (Visit 5) could be replaced by home health visit for sample collection and telehealth visit for clinical evaluation.

\*Administered everyday

+ Modified FLU-PRO Plus at Screen will be completed on site to determine if patient meets inclusion criterion

## 3.6 Primary Objective

Primary Objectives:

# BOSS-Covid-19 Study (BOSS-001)

1. To evaluate if treatment with 3 g TQ Formula (500 mg per capsule, 3 capsules BID) given orally on outpatient basis can significantly reduce median time to sustained clinical response compared to placebo in participants with COVID-19 infection treated in the outpatient setting. Sustained clinical response is defined as a reduction of scores to </= 2 on all symptoms of the Modified FLU-PRO Plus and should be remaining </= 2 for at least three days.
2. To evaluate the safety and tolerability of TQ Formula (500 mg oral capsule, 3 capsules BID) when given to participants with COVID-19 infection

## 3.7 Secondary Objective

1. To compare the viral load profile over time (from baseline through to Day 14) between treatment with 3 g TQ Formula (500 mg per capsule, 3 capsules BID) given orally on outpatient basis and placebo in participants with COVID-19 infection treated in the outpatient setting
2. To compare the percentage of RT-PCR negative/undetectable (i.e., viral clearance) on Day 7 and Day 14 in participants taking 3 g TQ Formula (500 mg per capsule, 3 capsules BID) versus participants taking placebo
3. To compare the duration and severity of symptoms (measured by Modified FLU-PRO Plus) over time from Day 1 through Day 14 in total FLU-PRO Plus symptom severity score overall and in sub-domain scores (namely, Nose, Throat, Eyes, Chest/Respiratory, Gastrointestinal, Body/Systemic, Taste/Smell), between treatment with 3 g TQ Formula (500 mg per capsule, 3 capsules BID) given orally on outpatient basis and placebo in participants with COVID-19 infection
4. To investigate if there exists an association between viral load and symptom severity by study arm and if such associations change overtime.

### Exploratory objectives:

1. To evaluate the basic pharmacokinetics of TQ Formula active ingredient (thymoquinone) at the same time points (Days 1, 7, and 14) in participants with COVID-19 infection.
2. To explore the effect of TQ Formula on inflammatory cytokines, coagulation factors and effector immune cells at same time points (Days 1, 7, and 14) in participants with COVID19 infection.

# BOSS-Covid-19 Study (BOSS-001)

## 4 Study Endpoints

### 4.1 Efficacy Endpoints

#### 4.1.1 Primary Efficacy Endpoint:

Measurement of the difference in median time to sustained clinical response in participants taking 3 g TQ Formula (500 mg per capsule, 3 capsules BID) versus participants taking placebo.

Sustained clinical response is defined as a reduction of scores to  $\leq 2$  on all symptoms of the Modified FLU-PRO Plus and sustained  $\leq 2$  for at least three days.

#### 4.1.2 Secondary Efficacy Endpoints

1. Measurement of change in quantitative viral load from baseline, Day 7, and Day 14 using RT-PCR in participants taking 3 g TQ Formula (500 mg per capsule, 3 capsules BID) versus participants taking placebo with COVID-19 infection.
2. Percentage of negative/undetectable RT-PCR (i.e., viral clearance) on Day-7 and Day-14 in participants taking 3 g TQ Formula (500 mg per capsule, 3 capsules BID) versus participants taking placebo
3. Measurement of severity of, and change in, Covid-19 symptoms per total score as well as sub-scores (Nose, Throat, Eyes, Chest/Respiratory, Gastrointestinal, Body/Systemic, Taste/Smell) measured through Modified FLU-PRO Plus from Day 1 through Day 14 in participants with COVID-19 infection treated either with 3 g TQ Formula (500 mg per capsule, 3 capsules BID) or placebo.
4. Correlation Coefficient of quantitative viral load and symptom severity at baseline, at Day 7, and Day 14 in participants taking 3 g TQ Formula (500 mg per capsule, 3 capsules BID) versus participants taking placebo

#### 4.1.3 Other Efficacy Endpoints

The endpoints for the exploratory aims are the following:

1. Measurement of thymoquinone and metabolites' concentration in the plasma on day 1, Day 7 and 14 using HPLC in patients treated with TQ Formula.
2. Measurement of the inflammatory cytokine production, coagulation factors and the various effector immune cell subsets in the Peripheral Blood Mononuclear Cells (PBMC) of all patients on Day 1, Day 7 and Day 14 using FACS.

If other analyses are needed beyond the endpoints mentioned above, this plan will be revised.

## 4.2 Safety Endpoints

Number of overall adverse events, related adverse reactions, and hospitalizations reported in participants taking 3 g TQ Formula (500 mg per capsule, 3 capsules BID) versus participants

# BOSS-Covid-19 Study (BOSS-001)

taking placebo. All AEs/SAEs will be captured throughout the study as per schedule of assessments.

## 5 Statistical Methods

### 5.1 General Statistical Methods

Summary tables (descriptive statistics and/or frequency tables) will be provided for all baseline and on study variables, efficacy variables, and safety variables, as appropriate. Continuous variables will be summarized with descriptive statistics (n, mean, standard deviation, range, and median). Frequency counts and percentage of subjects within each category will be provided for categorical data when appropriate in frequency and contingency tables.

### 5.2 Analysis Sets

The following are the main analysis datasets defined in the study protocol:

- Full Analysis Dataset: The Full Analysis Set (FAS) is defined as all randomized participants who receive at least one dose of study intervention.
- Final Dataset for Primary Objectives (FDPO): FDPO is defined as all randomized evaluable participants regardless of whether or not they received the assigned treatment regimen according to the evaluability definition above.
- Intent-to-treat (ITT) dataset: ITT dataset is defined as all randomized patients regardless of their adherence to or completion of the study regimen. This dataset includes all randomized participants even if they do not receive any dose or they withdraw from the study without completing the regimen or experience protocol violations.
- Safety Analysis Dataset: The Safety Analysis Set is defined as participants who take at least one dose of study intervention.
- Per-Protocol Analysis Dataset: The Per-Protocol Analysis Set (PP) is defined as all participants in the FAS who complete all visits up to and including Day 14, are compliant with study medication and do not have any major protocol violation. Major protocol violations will be identified prior to breaking the blind.

### 5.3 Statistical Analyses

#### 5.3.1 Demographic and Baseline Characteristics

Demographic and baseline characteristics data will be summarized with descriptive statistics. Continuous variables will be summarized with n, mean, standard deviation, minimum, maximum and median. Frequency counts and percentage of subjects within each category will be provided for categorical data.

# BOSS-Covid-19 Study (BOSS-001)

## 5.3.2 Primary Analyses

Primary estimand-1 is defined to be the difference of median time to sustained clinical response between participants taking 3 g TQ Formula (500 mg per capsule, 3 capsules BID) and participants taking placebo regardless of whether or not they actually receive their assigned therapy (ITT) and assuming that their hospitalization and treatment discontinuation rates will be similar. Possible intercurrent events for this estimand can be, though expected to be quite rare, hospitalization (i.e., transitioning from outpatient status to inpatient status) and treatment discontinuation, both of which may lead to potential missing data or change in the primary measures. The study participants will be reminded to submit their Modified FLU-PRO Plus questionnaires even after these intercurrent events to avoid missing data as much as practically possible. Hospitalization-free, while-on-study and per-protocol treatment versions of the above estimand will also be considered within each population definitions above.

Median time to sustained clinical response for the treatment and placebo arms will be estimated using the Kaplan-Meier method and Log-rank test will be utilized to compare the time to sustained clinical response distributions between the two study arms using LIFETEST procedure in SAS Version 9.4 ® (SAS Institute, Cary, North Carolina, USA). Events will be defined as cases that attain sustained clinical response while on study and time to event will be calculated as the days from the date of symptoms onset to the date that all symptoms are below Level-2 ('A little bit') on the Modified FLU-PRO Plus questionnaire. Patients who do not attain to clinical response while on study will be censored on Day-21 or on the day they are off study before Day-21 due to other reasons.

Although all analyses will be conducted based on the intent-to-treat principle, sensitivity analyses based on the adherence to the protocol regimen will also be carried out for the primary as well as secondary objectives. Sensitivity analyses will also include hospitalization-free, while-on-study, and per-protocol treatment cohorts as described above.

Primary Estimand-2 for the safety objective is the difference of frequencies of Adverse Events and Serious Adverse Events between participants taking 3 g TQ Formula (500 mg per capsule, 3 capsules BID) and participants taking placebo regardless of whether or not they actually receive their assigned therapy (ITT) and assuming that their hospitalization and treatment discontinuation rates will be similar. The above mentioned intercurrent events are also applicable for this safety estimand. Therefore, hospitalization-free, while-on-study and per-protocol treatment versions of the above estimand will also be considered within each population definitions above.

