5.5 STRATEGIES FOR RECRUITMENT AND RETENTION

Participants will be identified through Covid-19 screening tests at participating study sites and potential referral centers. Individuals who test positive for Covid-19 will be contacted and asked if they wish to participate in a research study. Upon signing of the informed consent, each patient will undergo screening procedures to determine eligibility for the study. Each study site may develop a site-specific recruitment plan if required.

Up to 60 participants will be equally randomized to receive either TQ Formula 3g (3x 500 mg capsules, BID) or matching placebo capsules (See section 9.2 for sample size determination details). There will be between 2-4 US sites participating in this study. The sites will be outpatient clinics that are currently testing/treating Covid-19 patients.

It is anticipated that each site will recruit approximately 4-5 participants per week. Based on this anticipated accrual rate, 2 sites should be able to complete recruitment for this study within approximately 4-5 weeks.

Participants will be compensated a reasonable amount for their study time and out of pocket costs such as parking, transportation or food on visit days will be reimbursed.

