9.2 SAMPLE SIZE DETERMINATION

For statistical analysis purposes, sustained clinical response is defined as a reduction to a score of ≤ 2 on all symptom scores on the Modified FLU-PRO Plus questionnaire.

Based on the median time to sustained clinical response reported by CDC [122], the expected median time to response in the placebo arm will be approximately 16 days from the onset of symptoms in outpatients. With a sample size of 20 in each arm, a difference in median time to sustained clinical response of 10 days between the intervention arm and the placebo arm will be able to be detected with 81.5% statistical power with 5% Type-1 error rate. Median time to sustained clinical response will be estimated based on 21-day follow-up. With an attrition expectation of around 20%, the planned accrual is 26 patients in each arm and potentially up to 30 patients.

Patients will be randomly assigned to one of the two study arms, using a block-randomization with a block size of 4, stratified by the enrolling sites. No other stratifications will be used. Randomization block size will be kept fixed at 4 as this is a small study and making the block size random as well is not needed. An unblinded statistician will generate a randomization list.

Definition of Evaluability for Primary Objectives: The double blind, placebo controlled two-arm clinical trial is designed to enroll up to 60 patients equally randomized between the two arms of the study. An evaluable patient is defined as a patient who has received at least one dose of the intervention drug or placebo.

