9.4 STATISTICAL ANALYSES

9.4.1 GENERAL APPROACH

Categorical variables will be presented as frequencies and percentages with column and row percentages in 2x2 or Rx C tables as appropriate. Association between two nominal variables will be investigated using Chi-Square tests and/or Fisher's Exact test as needed. Cochran Armitage trend-test may be included among the possible tests to investigate the possible trend between one ordinal factor and one binary factor. Association between two ordinal variables may be investigated through Non-zero Correlation test. Continuous variables will be presented as mean and standard deviation as well as five-number summary (minimum, first quartile, median, third quartile, and maximum). Range and inter-quartile range may also be explicitly provided as needed. Distribution of a continuous variable among the levels of a binary or polynomial factor will be investigated graphically through boxplots and through Wilcoxon-MannWhitney test and/or Kruskal Wallis tests. Association between two continuous variables will be described through scatter plots and Pearson's and Spearman's correlation coefficients as appropriate. When needed, normality assumption of a given continuous variable will be tested using Shapiro-Wilk Normality test. The details of the statistical models addressing each and every primary, secondary, and exploratory objectives along with primary predictors and control variables will be provided in a corresponding Statistical Analysis Plan (SAP). In this protocol document, a general analysis and statistical testing approach will be provided, and the details will be left for the study SAP.

In all comparisons and tests, a two-sided p-value will be used and a Type-1 error rate of 0.05 will be used to indicate significance. No multiplicity correction will be employed for statistical tests addressing the two primary objectives. Similarly, no multiplicity correction will be employed for statistical tests addressing the secondary and exploratory objectives as the results from these objectives must be considered within the hypotheses generating context.

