9.4.2 ANALYSIS OF THE PRIMARY EFFICACY ENDPOINT(S)

The primary endpoint of this clinical trial is the estimate of the median time to sustained clinical response for the treatment and placebo arms. Kaplan-Meier method will be used to estimate the time to sustained clinical response distribution and log-rank test will be utilized to compare the time to sustained clinical response distributions between the two study arms. Events will be defined as cases that attain clinical response while on the follow-up window and time to event will be calculated as the days from symptom onset to the resolution of symptoms to zero based on the Modified FLU-PRO Plus questionnaire. Patients who do not attain to clinical response while on the follow-up window will be censored on Day-21 or on the day they are off study before Day-21 due to other reasons. Although all analyses will be conducted based on the intent-to-treat context, sensitivity analyses based on the adherence to the protocol regimen will also be carried out for the primary as well as secondary objectives.

When appropriate, Last-Value-Carried-Forward (LVCF) imputation approach will be utilized for the missing values. As this is a small study that has a short span of enrollment and treatment windows, we do not anticipate excessive missing values; however, missingness structure will still be analyzed as to whether or not the missingness is Missing Completely at Random (MCAR), or Missing at Random (MAR), or Not-Missing at Random (NMAR). In the even of MCAR and MAR, sensitivity analyses will be carried out by using Multiple Imputation (MI) techniques.

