#### Analysis plan for Exploratory Aim-2:

Descriptive and graphical statistics will be used to present the distribution of the inflammatory cytokine production, coagulation factors and the various effector immune cell subsets in the Peripheral Blood Mononuclear Cells (PBMC) of all patients on Day 1, Day 7 and Day 14 using FACS within each study arm. These markers will also be compared for differential distribution between the arms using Wilcoxon-Mann-Whitney test. Like above, to compare the change over time in these markers, Random Coefficients Models will be utilized where each of these markers will be the dependent variable and study arm and time will be main predictors.

In addition to the primary analysis described in Section 5.3.2 above, Response Free Survival (RFS) distributions will be compared using Cox-Proportional Hazards Models between the two

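### Randomisation is blocked within site but the primary log-rank is not stratified by site; stratifying it, and fixing the supplementary Cox covariates, is an optional efficiency improvement

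*SAP*

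**What the plan says.** **Randomisation.** Protocol 9.2 allocates patients "using a block-randomization with a block size of 4, stratified by the enrolling sites". SAP 3.4 says the same: "using a block randomization with a block size of 4 independently within each center". On the number of sites, Protocol 5.5 states: "There will be between 2-4 US sites participating in this study".

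**Primary test.** SAP 5.3.2: "Log-rank test will be utilized to compare the time to sustained clinical response distributions between the two study arms using LIFETEST procedure". Protocol 9.4.2 agrees: "log-rank test will be utilized to compare the time to sustained clinical response distributions between the two study arms". Neither names a stratum or a site term, and neither gives a reason for leaving site out. Protocol 9.4.1 promises that the SAP will set out the control variables for every objective.

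**Additional model.** SAP 5.3.4, under Other Analyses, adds: "Response Free Survival (RFS) distributions will be compared using Cox-Proportional Hazards Models". Covariates are given by example only (sex, baseline viral load, age, and so on), with two or three expected. Site and baseline symptom score are not named. Protocol 9.4.7 is equally open. SAP 6.3 shows that the symptom questionnaire is completed at screening and at enrolment, so a baseline score exists.

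**Timing.** Under SAP 7.7 the efficacy data are locked and the statistician is then unblinded for a preliminary efficacy report. No section requires the Cox covariates to be fixed before that step.

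**The concern.** Blocking within site balances the arms inside each site, so differences between sites contribute almost nothing to the difference between arms. An unstratified log-rank still counts that between-site variation in its variance. It also compares curves that mix fast and slow sites, which pulls the apparent effect towards the null. If sites recover at different speeds, the test is therefore conservative and gives up power that the design has already paid for.

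Power is at stake, and the trial has little to spare: it is planned at 81.5% on 20 patients per arm. Protocol 5.5 expects that two sites could complete recruitment, and two sites is the setting where the loss would be largest.

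The second issue is smaller. A covariate chosen after unblinding could be reported as planned, because the SAP's list is open.

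**Working it through.** **Inputs from the documents.** Two-sided alpha 0.05 (Protocol 9.4.1). Medians 16 days on placebo and 6 on active (a 10-day difference), 20 per arm, 81.5% power and 21-day follow-up (SAP 3.2). Accrual, also SAP 3.2: "With an attrition expectation of around 20%, the planned accrual is 26 patients in each arm". Blocks of 4 within 2-4 sites.

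**The plan's own figure.** With exponential times the hazard ratio is 6/16 = 0.375.

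- Freedman, all 40 patients counted as events: √40 × (1 − 0.375)/(1 + 0.375) − 1.96 = 2.87 − 1.96 = 0.91, giving 82.0%. This is close to 81.5%.
- Events limited to 21 days: 20 × (1 − 2^(−21/16)) + 20 × (1 − 2^(−21/6)) = 11.9 + 18.2 = 30.2 (before rounding). Schoenfeld: √(30.2/4) × ln(16/6) − 1.96 = 0.74, giving 76.9%.
- Attrition: 20/0.8 = 25 per arm, against 26 planned.

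None of these calculations has a site term.

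**The two tests.** At each event day, U adds d₁ − d·n₁/n and V adds d(n₁/n)(1 − n₁/n)(n − d)/(n − 1). The unstratified test rejects if U²/V > 3.84 over all patients. The stratified test computes U and V within each site and rejects if (ΣU)²/ΣV > 3.84.

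**Simulation.** 6,000 trials per scenario; blocks of 4 dealt evenly over the sites; exponential times recorded in whole days; censoring at day 21. Site log-hazards are evenly spaced over an assumed total spread, slowest to fastest. Four designs were run:

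- 52 patients (unstratified power 86-87% with no site difference);
- 40 patients (76-77%, in line with the 76.9% above);
- 52 with 20% excluded (78%);
- 52 with 20% censored early (83-84%).

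Stratified minus unstratified power, in percentage points, as the range over the four designs:

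| Assumed spread | 2 sites | 3 sites | 4 sites |
|---|---|---|---|
| none | −1.3 to −0.7 | −3.0 to −1.8 | −4.1 to −2.3 |
| 1.5-fold | −0.2 to +0.9 | −2.3 to −0.7 | −3.5 to −1.9 |
| 2-fold | +2.5 to +3.1 | +0.3 to +0.8 | −1.4 to −0.8 |
| 3-fold | +8.4 to +10.6 | +4.3 to +4.8 | +1.8 to +2.6 |

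Monte Carlo error of a difference is 0.2-0.5 points. Repeat runs with separately written code (2,000-3,000 trials per cell) agreed to within about 1.5 points.

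**Type I error** (medians 16 and 16). Unstratified: 4.5-6.0% with no site difference and 3.4-4.4% at 3-fold. Stratified: 4.5-6.1% throughout. Monte Carlo error is about 0.3 points. There is no inflation, only conservatism when sites differ.

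**Variations** (52 patients; 2/3/4 sites; points):

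| Assumed spread | Time from onset (1-7 days added) | Unequal sites (10/3, 8/4/1, 7/4/1/1 blocks) |
|---|---|---|
| none | −0.7/−1.4/−3.0 | −0.9/−1.3/−2.2 |
| 2-fold | +2.7/+0.7/−1.1 | +1.4/+1.0/−0.6 |
| 3-fold | +8.5/+4.3/+2.4 | +6.7/+3.9/+2.0 |

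Pooling a 4-patient site with the next smallest changes the unequal-site results by less than 1 point.

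**Baseline score in the Cox model** (site-stratified, with and without the score; 3,000 trials; 40 and 52 patients). Adding the score changes power by −0.8 to −0.3 points if it is not prognostic, +0.9 to +2.8 at an assumed log-hazard of 0.25 per SD, and +5.8 to +9.7 at 0.5 per SD.

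**The case against.** The strongest reply is that the primary test is already specified, down to the SAS procedure, and is valid. An unadjusted primary test with covariates kept for a separate model is a coherent plan, and only the rationale is missing. Estimand-1 is a difference in overall medians. An unstratified log-rank compares those same marginal curves, whereas a stratified test compares arms within site. Every gain depends on a site spread that the documents do not give. With 4 sites, stratifying loses power at no difference, 1.5-fold and 2-fold, and wins only a little at 3-fold. With 3 sites it gains less than 1 point at 2-fold. All of this stands, and it is why the point is minor.

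What remains is that site is already a design factor, the number of sites may well be two, and at two sites the trade is lopsided: about 1 point lost against 8-11 gained at a 3-fold spread.

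Three stronger readings are tempting, and the documents do not support them:

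- *The mismatch invalidates the primary p-value.* It does not; the unstratified test holds its level or falls below it.
- *The open covariate list lets the trial result be chosen.* The Cox model sits under Other Analyses and cannot change the primary decision. No section proposes picking the most favourable model, and SAP 2.2 requires unplanned analyses to be identified. That rule does not, however, fix the covariates.
- *Site and baseline score are excluded from the Cox model.* They are only unnamed; the open list would allow them.

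**Conclusion.** The concern holds as a minor efficiency point. If sites do not differ, stratifying changes power by about −1 point with 2 sites and −2 to −4 points with 4. At a 3-fold spread it gains about 8-11 points with 2 evenly sized sites (about 7 if sizes are unequal), 4-5 with 3 sites and 2-3 with 4. With 4 sites it is a small net loss up to about a 2-fold spread, so the benefit lies mainly with 2, or perhaps 3, sites that differ.

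These figures assume exponential times at the planned medians and an invented range of site effects. The direction is stable across the designs tried; the size depends on the assumed spread. The gain from adding the baseline score likewise rests on an assumed prognostic strength and concerns only the supplementary model.

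**What to change.** In SAP 5.3.2:

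- Stratify the primary log-rank by site (`STRATA site / GROUP=arm` in LIFETEST).
- Before unblinding, pool any site with fewer than 4 patients with the next smallest site.
- Keep the overall Kaplan-Meier medians for estimand-1, and say that they are marginal while the test compares arms within site.
- Report the unstratified log-rank as a sensitivity analysis. SAP 7.4, which says sensitivity analysis does not apply, needs a matching edit.
- Name the downside: up to about 4 points of power with 4 sites that do not differ.

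If the sponsor prefers the unstratified test as primary, one sentence giving the reason would close the gap.

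In SAP 5.3.4, stratify the additional Cox model by site. Replace the open list with a fixed set of two or three covariates that includes the baseline total Modified FLU-PRO Plus score, signed off before the efficacy unblinding described in SAP 7.7.

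The cost is a few sentences and one line of code, with no new data, plus the possible power loss stated above.
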